## **17 Other Practical Considerations**

### **17.1 Investigator's Brochure**

The Investigator's Brochure contains a summary of the pre-clinical and clinical data. The same confidentiality procedures apply for the Investigator's Brochure as for the protocol.

The Investigator's Brochure will be included in the Investigator file. The Investigator will sign a receipt form.

### **17.2 Final Clinical Trial Report**

The CSR will be written by the CRO following the ICH guidelines requirements. It will be approved and signed by the Coordinating Investigator and Almirall representatives according to internal SOPs.

The CSR will be audited by the CRO and/or Almirall before issuing the final version.

The final version of the electronic CSR will be e-published (hyperlink, bookmarks, etc.) including all appendices according to ICH Guidelines.

The summary of the CSR will be sent to all the Investigators participating in the clinical trial.

### **17.3 Protocol Amendments**

Modifications of the original protocol are referred to as "amendments" to the trial protocol. Modifications of the original protocol may only be made with Almirall approval. Two types of amendment maybe produced:

- Substantial Amendments (related to the safety or physical or mental integrity of the patients, scientific value of the trial, conduct or management of the trial or the quality or safety of any IMP used) must be notified to the IRB and/or Competent Authorities and approved by them before implementation.
- Non-substantial Amendments do not require notification but should be recorded and be available on request for inspection at the trial site and/or Sponsor premises as appropriate.

### **17.4 Protocol Deviations**

Any protocol deviations during the conduct of the trial will be recorded by the CRA/Monitors as detected or derived from data collected in the clinical database.

Relevant deviations will be promptly reported to Almirall after detection. Major protocol deviations will be included in the corresponding listing of the CSR.

Additionally, protocol deviations will be reported to the IRBs/IECs and/or Competent Authorities according to the local regulation in each country.

## 19 Appendices

1. Highly Effective Methods of Birth Control
2. Patch test for the Assessment of Contact Dermatitis

## Appendix 1, Highly Effective Methods of Birth Control

Highly effective methods of birth control (ref. CTFG 2014 guidance document):

- Intrauterine device, intrauterine hormone-releasing system or bilateral tubal occlusion or ligation
- Combined (estrogen and progestogen containing) hormonal contraception associated with inhibition of ovulation (oral, intravaginal or transdermal)
- Progestogen-only hormonal contraception associated with inhibition of ovulation (oral, injectable or implantable)
- Vasectomized partner. Female patient must agree to implement one of the other highly effective methods of birth control if her lifestyle/partner changes
- Sexual abstinence

### Notes

(1) Low user dependency methods from at least 3 months before trial screening

(2) Only provided that partner is the sole sexual partner of the WOCBP trial participant and that the vasectomized partner has received medical assessment of the surgical success.

(3) Only if defined as refraining from heterosexual intercourse during the entire period of risk associated with the study treatments (from Day1 to at least 30 days after the last dose of the investigations product).

## Appendix 2, Patch Test for the Assessment of Contact Dermatitis

In the event the patient experiences a skin reaction of such nature or severity that an allergic contact dermatitis is suspected, the patient can be treated with topical treatment with corticosteroids (eg, betamethasone) and oral antihistamines and should temporally discontinue the study medication. The event should be documented as an adverse event and the medication given recorded. The patient should be re-challenged using the assigned study medication (patch test in the back) to confirm or rule out contact dermatitis. If the diagnosis of allergic contact dermatitis is confirmed the patient may have an additional patch test with both the tirbanibulin-containing ointment and the vehicle base.

The patch test will be performed at least 2 weeks after last treatment or discontinuation of the study medication. Patches will be applied to untreated areas on the back for 48 hours. Readings will be performed approximately 15 to 30 minutes and 48 hours following the removal of the patches. At the investigator's discretion, a facultative additional reading might be performed at 96 or 120 hours after removal of the patches if an equivocal reaction is observed at the previous reading. If allergic contact dermatitis is confirmed the patient will discontinue permanently the study medication, on the contrary the patient can be treated with the study medication if necessary.

## **Letter of Protocol Clarification - *Administrative Change 1***

Protocol Title: A Phase 3, Multicenter, Open-label, Single-arm Study to Evaluate the Safety and Tolerability of Tirbanibulin Ointment 1% Applied to a Field of Approximately 100 cm^2 on the Face or Balding Scalp in Adult Patients with Actinic Keratosis

Protocol Number: M-14867-32

Date: 03-JAN-2023

---

Dear Investigator(s),

After the issuance of M-14867-32 Protocol Version 2.0 dated 21 March 2022, and for the correct development of the trial, clarifications were determined to be needed in relation to the completion of patient's eDiary.

At section "12.1.3 Patient Diary", the protocol details the usage of an electronic diary (Study App) to record daily the study treatment application dates and times of application for the above-mentioned study, to be completed by subjects. However, in case of need, a paper diary was also developed as an alternative when needed.

This contingency plan was not included in the protocol by mistake, and therefore it is not listed in the section "12.1.1 Identification of the Trial Data Source" as a valid source document.

The mentioned paper diary was developed, submitted, and approved by the Ethics Committee prior to implementation at sites. However, since this contingency plan was not included in the Protocol, there was the need to issue this clarification letter to specify that both the Study App and the paper diary, when applicable, are considered trial data sources for study treatment application dates and times.

Since this is a minor correction, an amendment to the Protocol is not expected.

DocuSigned by:

PPD

 Nombre del firmante: PPD

Motivo de la firma: He revisado este documento

Hora de firma: 10-ene.-2023 | 13:21:32 CET

PPD

DocuSigned by:

PPD

 Nombre del firmante: PPD

Motivo de la firma: Apruebo este documento

Hora de firma: 10-ene.-2023 | 14:13:10 CET

PPD

PPD

*International Clinical Trial Manager**cc: Trial Master File*

PPD

*Global Clinical Lead*

1 ABBREVIATIONS

AE	Adverse event
AESI	Adverse event of special interest
AK	Actinic keratosis
ATC	anatomical therapeutic chemical
CI	Confidence interval
COVID-19	Coronavirus disease 2019
CRF	Case Report Form
CRO	Clinical Research Organization
DMP	Data Management Plan
ECG	Electrocardiogram
eCRF	Electronic case report form
EoS	End of Study
EoT	End of Treatment
ESI	Event of special interest
ET	Early termination
ICF	Informed Consent Form
PE	Physical examination
PT	preferred term
Q1	first quantile
Q3	third quantile
SAE	Serious adverse event
SAP	Statistical Analysis Plan
SAS	Statistical Analysis System®
SE	standard error
SD	standard deviation
SOC	system organ class
TF(s)	Treatment Field(s)
TEAE	Treatment-emergent adverse event
TESAE	treatment emergent serious adverse events

M-14867-32

Statistical Analysis Plan Status: Version (17 Jan 2023)

TLF tables, listings, and figures

WHO-DD World Health Organization Drug Dictionary

M-14867-32

Statistical Analysis Plan Status: Version (17 Jan 2023)

2 CLINICAL TRIAL PERSONNEL

A detailed list of team members with respective role and contact information is maintained separately in the main study contact list.

3 INTRODUCTION

3.1 Description of this Document

This Statistical Analysis Plan (SAP) describes the planned analysis and reporting for sponsor clinical protocol M-14867-32. The analyses described in the SAP are based upon the protocol Version 2.0 dated 21-Mar-2022. In case of discrepancies between the protocol and the SAP, the SAP will be used to guide the statistical analysis.

This SAP has been developed prior to database lock and final analyses. All final analyses will be performed after the clinical trial data are entered into the database, any discrepancies in the data are resolved, the database is locked, and following the signature of the SAP.

The signature of this SAP will act as the assignment of each patient within the populations.

3.2 Trial Design

This is a Phase 3, multicenter, open-label, single-arm trial to evaluate safety and local tolerability of tirbanibulin ointment 1% administered topically for 5 days over a field of approximately 100 cm² on the face or balding scalp in adult patients with actinic keratosis (AK). The study consists of a 4-week (28-day) Screening Period, a 5-day Treatment Period, and a Response Assessment Period of approximately 7 weeks (see [Table 1](#), Schedule of Assessments):

- During the Treatment Period, patients will apply tirbanibulin ointment 1% once daily for 5 days beginning on Day 1.
- All patients will be evaluated for safety, tolerability, and the presence of AK lesions in the treatment field (TF) until completion of the Response Assessment Period at Day 57.

Enrollment will be controlled such that the trial population is representative of the population expected to use the product in terms of age and treated area. A minimum of 50% of patients older than 65 years old will be included and approximately two-thirds of the patients will be treated for AK lesions on the face and one-third on the scalp.

M-14867-32

Statistical Analysis Plan Status: Version (17 Jan 2023)

Table 1 Schedule of Assessments

Period	Screening*	Treatment		Response Assessment				
Visit(s)	1	2	At home, once-daily self-administration ^m	3	4	5	6	7
Day(s)	-28 to -1	1 (Baseline)	2 to 5	5	8	15	29	57
Visit Time Window (days)	None	None		None	±2	±2	±3	±3
Informed consent	X							
Inclusion & exclusion criteria	X	X ^a						
Demographics	X							
Medical/surgical history	X							
AK history/AK treatment history	X							
Prior and concomitant medications/therapies	X	X ^a		X	X	X	X	X
Fitzpatrick skin type	X							
Treatment field identification ^k	X	X ^a						
Vital signs ⁱ	X	X ^a						X

M-14867-32

Statistical Analysis Plan Status: Version (17 Jan 2023)

Period	Screening*	Treatment		Response Assessment					
		1	2	At home, once-daily self-administration ^m	3	4	5	6	7
Visit(s)									ET/EoS
Day(s)	-28 to -1		1 (Baseline)	2 to 5	5	8	15	29	57
Visit Time Window (days)	None	None			None	±2	±2	±3	±3
Physical examination ^d	X								X
Clinical chemistry, hematology, urinalysis	X								X
ECG ^b	X								X
Pregnancy test for WOCBP ^c	X	X ^a							X
Study App installation and instructions		X ^a							
Study App review by Investigator ⁱ					X				
Study drug application		X	X						
Instructions for self-administration and study drug dispensing		X							
Study drug return					X ^e				
Weight of study drug packets ^f		X			X				
Standardized photography of the treatment field	X	X ^{a,l}			X	X	X	X	X
AEs ^g	X	X	X		X	X	X	X	X ^h

M-14867-32

Statistical Analysis Plan Status: Version (17 Jan 2023)

Period	Screening*	Treatment		Response Assessment					
		1	2	At home, once-daily self-administration ^m	3	4	5	6	7
Visit(s)									ET/EoS
Day(s)	-28 to -1		1 (Baseline)	2 to 5	5	8	15	29	57
Visit Time Window (days)	None	None			None	±2	±2	±3	±3
Treatment Field location		X ^a		X	X	X	X	X	X
Focused dermatological exam of treatment field									
Local tolerability		X ^a			X	X	X	X	X ^b
Hypo- and hyperpigmentation and scarring		X ^a			X	X	X	X	X ^b
AK Lesion count in the TF	X	X			X	X	X	X	X

Abbreviations: AE=adverse event; AK=actinic keratosis; ECG=electrocardiogram; ET=Early Termination; EoS=End of Study; ICF=informed consent form; TF=treatment field; WOCBP=women of child-bearing potential.

* Patients who require a washout period from prohibited concomitant treatments should be seen and sign the ICF prior to the Screening visit, to ensure the necessary washout before starting treatment. No trial assessments will be performed on that date and the Screening visit will be scheduled according to the washout length required for the specific medication stopped.

^a Assessments/procedures performed before treatment administration. Day 1 evaluation will serve as a Baseline for these assessments.

^b Patients must be in a supine position for 5 minutes prior to ECG.

^c Highly sensitive urinary pregnancy test performed at the clinical trial site.

^d Physical examination to include height, weight, and an assessment of head, eyes, ears, nose and throat, integumentary/dermatological, gastrointestinal, cardiovascular, respiratory, musculoskeletal, neurological systems, and an expanded dermatological examination to cover the sun-exposed areas, where photo-damage is likely. Height is measured only at screening.

M-14867-32

Statistical Analysis Plan Status: Version (17 Jan 2023)

^e On Day 5 patients are to bring all 5 study drug packets back to the site (used and unused) with their respective torn parts in the individual closed zipper storage bag provided in the study kit.

^f All study drug packets will be weighed together in their respective closed zipper storage bag before and after use (including the torn opening part).

^g At each study visit, patients will be asked a general question e.g. "How have you been since the last visit?" AEs will be recorded before assessments of local tolerability, hypo- and hyperpigmentation, and scarring in the TF. AEs will be reported separately from local tolerability signs.

^h All patients who have unresolved local tolerability signs, hypo- or hyperpigmentation, scarring in the TF, or treatment-related AEs at Day 57 will return for additional follow-up every 7 to 28 days until these have resolved, have returned to the baseline value, or are deemed stabilized by the Investigators.

ⁱ Measurement of vital signs will include blood pressure, heart rate, respiratory rate, and body temperature. Measurements of systolic and diastolic blood pressure will be performed after at least 5 minutes of rest in a supine position and preferably on the same arm.

^j Patients will complete a diary (Study App) to record daily dates and times of study treatment application. The diary (Study App) will be checked by the Investigator (or designee) at Visit 3.

^k TF identification (face/scalp)

^l Baseline photo is only required in case of any significant change from Screening is detected in the TF as per the Investigator judgement or if the quality of the image captured at Screening is not appropriate. If no photo is needed at baseline, then the screening photo will be considered the baseline assessment.

^m Study drug will be applied by the patient at home before study Visit 3 on Day 5, which will take place at the clinical site.

4 OBJECTIVES

4.1 Objectives

The primary objective of the trial is to evaluate the safety and tolerability of tirbanibulin ointment 1% when applied to a field of approximately 100 cm² on the face or balding scalp.

Additionally, the treatment effect of tirbanibulin ointment 1% when applied to a field of approximately 100 cm² on the face or balding scalp will be explored.

4.2 Endpoints

4.2.1 Safety Endpoints

Safety Endpoints

- Local Tolerability Assessment:
 - Number and proportion of patients with each local tolerability score by visit (0-3) for each individual sign (erythema, flaking/scaling, crusting, swelling, vesiculation/pustulation, and erosion/ulceration)
 - Maximum local tolerability score post baseline through all the visits for each individual sign
 - Time to maximum local tolerability score for each individual sign
 - Local tolerability signs composite score (0-18) by visit, defined as the sum of the scores graded from 0 to 3 on all six individual tolerability sign categories
 - Maximum local tolerability signs composite score post baseline through all the visits
 - Time to maximum local tolerability composite score
 - Proportion of patients with pigmentation and scarring in the TF through all the visits
- Number and proportion of patients with treatment emergent adverse events (TEAEs), treatment emergent serious adverse events (TESAEs), adverse events of special

interest (AESIs), and change from baseline in clinical laboratory data, and other safety assessments (vital signs, physical examinations [PEs], electrocardiograms [ECGs])

4.2.2 Exploratory Endpoints

- Absolute number, change from baseline, and percent change from baseline in AK lesion count from total lesions in the TF at each visit
- Absolute number, change from baseline, and percent change from baseline in AK lesion count, for lesions that were already present at baseline, from total lesions in the TF at each visit
- Absolute number and percent change of new lesions from total lesions in the TF at each visit

5 SAMPLE SIZE JUSTIFICATION

Approximately 125 patients will be screened to initiate treatment in approximately 100 patients.

With 100 patients and assuming an expected percentage of patients with at least one local tolerability sign of approximately 90%, the precision in the estimation of that percentage will be approximately 11%. The precision is defined as the width of the 95% confidence interval.

Furthermore, 100 patients will provide approximately 10% and 13% precision in the estimation of the percentage of patients with the local tolerability events of particular interest, specifically vesiculation/pustulation (assuming an expected percentage of 8%) and erosion/ulceration (assuming an expected percentage of 12%), respectively.

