### **7.2 Trial Rationale**

#### **7.2.1 Rationale for Trial Design**

Since tirbanibulin ointment 1% is an approved product and there is no change in the formulation or posology, the main objective of this study is to evaluate the safety and tolerability of tirbanibulin ointment 1% applied over an extended field (100 cm^2) in adult patients with AK on the face or balding scalp.

The duration of the study considers both safety and efficacy. From a local tolerability perspective, most of the local signs are expected to be resolved by Day 29. However, the study duration is extended up to Day 57, in order to assess the treatment effect as exploratory endpoints.

In addition to the overall incidence of local tolerability events, the sample size considers detection of local tolerability signs of particular interest, specifically, vesiculation/pustulation and erosion/ulceration (see Section 11.1). When severe, these local tolerability signs can lead to permanent local events such as dyspigmentation or scarring.

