### **11.1 Sample Size Calculation**

With 100 patients and assuming an expected percentage of patients with at least one local tolerability sign of approximately 90%, the precision in the estimation of that percentage will be approximately 11%. The precision is defined as the width of the 95% confidence interval.

Furthermore, 100 patients will provide approximately 10% and 13% precision in the estimation of the percentage of patients with the local tolerability events of particular interest, specifically vesiculation/pustulation (assuming an expected percentage of 8%) and erosion/ulceration (assuming an expected percentage of 12%), respectively.

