6 STRUCTURE AND METHODOLOGY OF STATISTICAL ANALYSIS

6.1 Descriptive Statistics

Categorical variables will be summarized with counts (n) and percentages (%). For continuous variables, the number of non-missing observations (n), mean, standard deviation (SD), standard error (SE) of the mean, 95% confidence interval (CI) of the mean, median, first (Q1) and third (Q3) quartiles, minimum (min) and maximum (max) will be tabulated.

The 95% confidence interval for continuous data will be calculated using the normal approximation. If less than 30 patients with non-missing data are available (in a sub-group, if applicable) for a specific continuous data point, no confidence interval will be reported for this data point.

The 95% confidence interval for proportions will be calculated using the exact Clopper-Pearson method.

When applicable, summaries will be provided by visit of assessment.

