14.1 Local Tolerability Assessment

Local tolerability is assessed based on the review of the following signs in the treatment field: erythema, flaking/scaling, crusting, swelling, vesiculation/pustulation, and erosion/ulceration and will be evaluated both individually and as a composite score (total of the 6 individual scores ranging from 0 to 18). These signs will be graded as: 0=absent, 1=mild (slightly, barely perceptible), 2=moderate (distinct presence), and 3=severe (marked, intense). If one or more individual score is missing, the composite score will be set as missing.

The maximum local tolerability signs composite score across visits will be derived as the maximum local tolerability assessment (LTA) composite score observed post-baseline for a patient. The maximum local tolerability of individual signs across visits will be derived as the maximum LTA of an individual sign observed postbaseline for a patient.

Descriptive statistics will be presented for local tolerability signs composite score by visit, and for maximum local tolerability signs composite score across post-baseline visits. Frequency and percentages by visit of patients presenting any individual and composite local tolerability signs and associated CI based on exact Clopper-Pearson method will be presented. The presence of any individual and composite local tolerability sign is defined by a score of >0. Frequency and percentages by visit for specific local tolerability individual signs results and maximum local tolerability of individual signs across post-baseline visits will also be provided.

The 95% CI will be presented for the median of the maximum local tolerability composite score.

Figures presenting the number of patients with each local tolerability individual sign (absent/mild/moderate/severe) by visit, and a figure presenting the mean local tolerability composite score by visit will be produced.

The time to maximum LTA score for each individual sign and the time to maximum LTA composite score will be calculated as the time (in days) from the first dose of study treatment to the time of the first occurrence of the maximum LTA score observed post-baseline for each individual sign and composite score, respectively. That is, for each individual sign, time to maximum LTA, in days, will be calculated as follows:

(Date of first post-baseline occurrence of maximum LTA score for an individual sign – Date of first dose)

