Time to maximum composite LTA, in days, will be calculated as follows:

(Date of first post-baseline occurrence of maximum composite LTA score – Date of first dose)

If a patient's maximum composite/individual sign LTA score stays at 0 throughout the study, the patient will be considered censored at his last LTA score observation. The time to maximum composite/individual sign LTA will be analyzed using Kaplan Meier estimation, overall and by strata as applicable. The Kaplan Meier estimates will include the 25th, 50th (median), and 75th percentiles along with their 95% CIs. The standard errors (SE) will be computed using the Greenwood's formula. The CI for the median will be calculated as per Brookmeyer and Crowley and the CIs for the 25th and 75th percentiles will be calculated using the log-log transformation.

Survival curves will also be presented and all local tolerability assessments will be listed.

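### The stated 95% CI widths (about 11%, 10% and 13%) are narrower than the SAP's own Clopper-Pearson method gives at n=100, and no exact CI is listed for the overall incidence behind the sample size

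*SAP*

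**What the plan says.** Protocol 11.1 and SAP section 5 carry the same sizing statement. For 100 patients and an expected rate of about 90% with at least one local tolerability sign, "the precision in the estimation of that percentage will be approximately 11%. The precision is defined as the width of the 95% confidence interval". For the two signs of particular interest, "100 patients will provide approximately 10% and 13% precision in the estimation of the percentage of patients with the local tolerability events", with assumed rates of 8% (vesiculation/pustulation) and 12% (erosion/ulceration). The protocol names no interval method for proportions.

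The SAP does. Section 6.1 states: "The 95% confidence interval for proportions will be calculated using the exact Clopper-Pearson method". Section 6.2 makes all intervals two-sided with 95% coverage.

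On what was sized, Protocol 7.2.1 says: "In addition to the overall incidence of local tolerability events, the sample size considers detection of local tolerability signs of particular interest". On what will be reported, SAP 14.1 plans "Frequency and percentages by visit of patients presenting any individual and composite local tolerability signs and associated CI based on exact Clopper-Pearson method". Across visits it says that frequencies and percentages for "maximum local tolerability of individual signs across post-baseline visits will also be provided", with no interval mentioned. It also plans a 95% CI for the median of the maximum composite score.

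**The concern.** Precision is the only reason given for treating about 100 patients, and the SAP defines it as a full interval width. Once the SAP had chosen Clopper-Pearson, the widths taken over from the protocol should have been recalculated, and they were not. Even if every assumed rate is observed exactly, the reported exact intervals will be wider than the plan says.

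The second issue is related. A percentage with at least one sign, described in the protocol as an overall incidence, is most naturally a percentage over the whole post-baseline period. By-visit percentages cannot replace it, because a patient may be positive at one visit and negative at another, and no single visit gives the ever-positive proportion. The interval the trial was sized on is therefore not on the list of outputs.

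**Working it through.** **Inputs.** n = 100 and expected rates of 90%, 8% and 12% (SAP 5; Protocol 11.1). Two-sided 95% (SAP 6.2). Clopper-Pearson (SAP 6.1). Precision means full width (SAP 5).

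**Step 1: try to reproduce 11/10/13.** Start with the Wald width, 2 × 1.96 × √(p(1−p)/n):

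- 90%: 3.92 × √(0.90 × 0.10/100) = 3.92 × 0.0300 = 11.76 points
- 8%: 3.92 × √(0.08 × 0.92/100) = 3.92 × 0.02713 = 10.63 points
- 12%: 3.92 × √(0.12 × 0.88/100) = 3.92 × 0.03250 = 12.74 points

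These round to 12, 11 and 13. Full widths in points under other methods at n = 100:

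| Method | 90% | 8% | 12% |
|---|---|---|---|
| Stated | 11 | 10 | 13 |
| Wald | 11.76 | 10.63 | 12.74 |
| Jeffreys | 11.75 | 10.67 | 12.70 |
| Wilson | 11.91 | 10.89 | 12.81 |
| Mid-P | 11.91 | 10.84 | 12.84 |
| Agresti-Coull | 12.26 | 11.31 | 13.11 |
| Clopper-Pearson | 12.72 | 11.64 | 13.67 |

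None of these gives the stated set. Continuity-corrected Wald and Wilson, half-widths and a 90% confidence level do not give it either.

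**Step 2: the SAP's method.** The Clopper-Pearson lower limit is the 2.5% quantile of Beta(x, n−x+1), and the upper limit is the 97.5% quantile of Beta(x+1, n−x).

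- 90/100: 82.38% to 95.10%, width 12.72; 12.72 − 11 = 1.72
- 8/100: 3.52% to 15.16%, width 11.64; 11.64 − 10 = 1.64
- 12/100: 6.36% to 20.02%, width 13.67 (from unrounded limits); 13.67 − 13 = 0.67

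Relative to the stated widths, the shortfalls are 1.72/11 = 16%, 1.64/10 = 16% and 0.67/13 = 5%. In half-widths they are about 0.9, 0.8 and 0.3 points.

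**Step 3: does the word approximately close the gap?** Under Clopper-Pearson, 91/100 gives 12.20, and 11.0 is reached only at 93/100 (11.03). For the second rate, 7/100 gives 11.03, and only at 6/100 does the width round to 10 (10.37). For the third, 11/100 gives 13.21, so one event fewer is enough.

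**Step 4: scale.** For exact widths that merely round to 11, 10 and 13 (at or below 11.5, 10.5 and 13.5), the smallest n is about 121, 121 and 103, without rounding expected counts to whole patients. This shows the size of the gap and is not a proposal to enlarge the trial.

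**Step 5: planned outputs against the sized quantity.** Three outputs in SAP 14.1 come close:

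- By-visit percentages with any sign have an exact CI, but are not cumulative.
- The maximum score per sign across post-baseline visits is cumulative and gives per-sign incidence from its score-0 row, but no CI is stated.
- In the time-to-maximum analysis, if the maximum composite "score stays at 0 throughout the study, the patient will be considered censored at his last LTA score observation". This identifies patients who never had a sign, but supplies no binomial interval.

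The CI for the median maximum composite score concerns a score, not a proportion.

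**The case against.** The strongest reply is that nothing depends on the figures. No inference is planned, there is no width to achieve, and the reported intervals will be computed from the data whatever SAP 5 says. That stands, and it keeps the point minor.

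It can also be said that SAP 5 only repeats a planning basis that names no method, and that the figures are labelled approximate. This helps the 13% figure, which agrees with Wald, Wilson, Jeffreys and mid-P and, once rounded, with Agresti-Coull. It does not help 11% and 10%, which are too low under every method in the table. Nor does it explain leaving full widths in the SAP next to a method that does not produce them.

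On the second issue, SAP 5 never says the incidence is taken across visits. That reading combines the at-least-one-sign wording with the overall incidence of Protocol 7.2.1. SAP 6.1 could also be taken to cover any proportion reported. Both are fair, but SAP 6.1 says how an interval is calculated, not that one will be presented, and for categorical variables it promises only counts and percentages. It is also true that the counts can be recovered from planned outputs and the interval computed by hand. The omission is therefore one of listing, not of data.

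**Conclusion.** The concern holds, as a minor point. Under the SAP's own method the full widths at n = 100 are 12.7, 11.6 and 13.7 points against a stated 11, 10 and 13. The 11% and 10% figures are also 0.6 to 0.9 points low under Wald, Wilson, Jeffreys and mid-P; the 13% figure is low only against the exact method among those five. SAP 14.1 does not explicitly provide an exact interval for the across-visit incidence.

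These widths assume that the rates are observed exactly as expected and that all 100 patients contribute. Protocol 8.7 does not replace withdrawals; with 94 evaluable patients the exact widths would be about 13.2, 12.0 and 14.1. The second half rests on reading the sized percentage as cumulative over post-baseline visits. No estimate, error rate or conclusion is affected.

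**What to change.** In SAP 5, restate the widths as about 13%, 12% and 14% and say that they are Clopper-Pearson full widths at n = 100.

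In SAP 14.1, add a Clopper-Pearson 95% CI for the percentage of patients whose maximum post-baseline score is above 0, for three rows: any of the six signs, vesiculation/pustulation, and erosion/ulceration. Two additions are useful but optional: a count of how many of these patients already scored above 0 at baseline, since a score above 0 is not in itself a change, and a line in SAP Table 3 recording the revision.

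The cost is a short text correction and one table from data already collected. The only drawback is a slightly less favourable stated precision.
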